Primary Endpoints: 1. Lower Extremity Perfusion: Measurement of lower extremity perfusion at 4 weeks of continuous device usage. Peripheral perfusion will be measured at baseline, 48 hours, 1 week and 4 weeks. Ankle Brachial Index (ABI) and Skin Perfusion Pressure (SPP) will be used to evaluate perfusion status for all study participants.

2. Plantar Pressure: Measurement of plantar pressure compared to the standard (non-PulseFlow DF) offloading boot.

Secondary Endpoints:

The following secondary effectiveness endpoints will be evaluated but success will not be required for determining success of the study. 1) Balance: Improvement in balance and decrease in fall risk as measured using a validated body worn sensor system at baseline and 4 weeks. 2) Activity Measurement: Activity measurement during 48 hours of continuous daily physical activity using a validated body worn sensor system, measured at baseline and 4 weeks. 3) Gait assessment using validated wearable technology at baseline and 4 weeks.

Primary Safety Endpoints: 1) The occurrence of adverse events during the four (4) weeks of the study treatment that are possibly related, probably related, or definitely related to PulseFlow DF (e.g. deterioration in wound condition such significant increase in wound size, infection, etc, falls, serious adverse events) will be properly reported.

Other assessments: 1) Usability assessment 2) Patient perception of benefit and level of comfort (Scoring System); 3) Adherence to use of offloading boot; and 4) Others: Quality of life, fear of falling, frailty, etc.

The key goals of the proposed project are to test whether a specially designed compression device can improve lower extremity perfusion, whilst also simultaneously improving the balance and walking performance. We envision the use of this specially designed offloading device with compression capability will help reduce the incidence of diabetic foot ulcers in high-risk diabetic patients. In addition, we assumed the proposed device might enhance daily physical activity as well as walking performance. We will conduct a prospective clinical study to validate these hypotheses. Potential changes in walking and spontaneous daily physical activities will be assessed using validated technologies that include walking analyzer system, balance assessment using body worn sensors, and computerized pressure insoles.

Section E: Protocol Risks/Subjects

E1. Risk Category

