Assessment of user friendliness, acceptability, and perception of need: We will use a questionnaire tailored to the topic of this study to evaluate the perception of the target population in receiving benefit from the proposed technology. Subjects are asked to answer the questionnaire at the end of study. The questionnaire includes 11 items and allows assessing how target population perceives the need of such technology in management of their problem.

Other assessments: Other relevant assessments are Demographic/Health questionnaire, the Montreal Cognitive Assessment, the mobility-tiredness scale, Barthel Index, Depression Scale, fear of falling (Short-Falls Efficacy Scale – International), quality of life (Promise Global General Health Questionnaire), digital photography, Fried Frailty Criteria, Foot Questionnaire, Pain Assessment, Fall Log and Contact Agreement, Physical activity log, follow-up questionnaire, Shoe-fit test , subject’s perception assessment compared to standard shoe and RCW assessed using a 10 point Likert scale questionnaire.

PulseFlow DF: The PulseFlow device will be given to the subject. The research personnel will make sure that the subject is comfortable with the device and the device itself provides the offloading that is needed. The research personnel will also provide device education to the participants and will answer any questions that may arise.

Study Day 1, Visit 2 48-hour follow: All participants will be asked to return to clinic approximately 48 hours after visit 1. In this visit, (1) any adverse events will be assessed; (2) activity measurement (body sensor) will be returned; (3) PulseFlow DF data will be downloaded to ensure operability and patient compliance; and (4) further device education will be provided in case any issues have risen. We will take digital photographs of the participants feet and collect edema information.

Study Day 2, Visit 3 1-week follow-up: All participants will be asked to return to clinic approximately 1 week after visit 1. In this visit, (1) any adverse events will be assessed; and (2) PulseFlow DF data will be downloaded to ensure operability and patient compliance. Device education will be provided if needed. The participant will be asked to return the device at their next visit. We will take digital photographs of the participants feet and collect edema information.

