Study Day 3, Visit 4 4-week follow-up: All participants will be asked to return to clinic approximately 4 weeks after visit 1. In this visit, outcome assessment using similar assessments described for Study Day 0 will be performed. In addition, perception of benefit and user-friendliness of the PulseFlow DF® will be assessed using a questionnaire. We will take digital photographs.

Participants will be asked to wear a comfortable shirt which holds a small activity monitor (PAMSys) for a period of 48 Hours (2 days). Patients will be requested to return this device via a pre-paid FEDEX envelope

Study Day 4, Visit 5 Follow-up up to three months: Some participants may be contacted by the study coordinator approximately up to three months post the last study visit to document success of wound healing if they continue to use PulseFlow DF after 4 weeks as well as potential incident of re-ulceration, or incident of falls.

We will ask participants to provide an Emergency Contact.

We will ask participants if they would like to be contacted for further studies they may be eligible for.

****Please note that the protocol attached to Section S is from the University of Arizona. The PI initially established this protocol at U of A as it is an investigator initiated study. We have ensured that we have not included any references to U of A in this BCM protocol*****

Section G: Sample Size/Data Analysis

G1. Sample Size

How many subjects (or specimens, or charts) will be used in this study?

Local: 50 Worldwide: 50

Please indicate why you chose the sample size proposed:

We intend to employ a simple minimal risk research protocol to capture data required to realize the goals of this study. The results from this study will help us understand the real clinical needs and optimize the device specifications and form factor to fulfill these needs.

This is an initial proof of concept pilot study. The results of this study will allow for the calculation of an appropriate sample size for a larger proof of superiority (over current standard of care) trial.

G2. Data Analysis

Provide a description of your plan for data analysis. State the types of comparisons you plan (e.g. comparison of means, comparison of proportions, regressions, analysis of variance). Which is the PRIMARY comparison/analysis? How will the analyses proposed relate to the primary purposes of your study?

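### As scheduled, the two 48-hour activity recordings compare on-boot wear with an unrecorded mix of boot states, so their change does not estimate PulseFlow's effect on activity

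*Combined protocol and SAP*

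**What the plan says.** **Endpoint.** Section D (Secondary Endpoints) plans a 48-hour activity measurement "using a validated body worn sensor system, measured at baseline and 4 weeks". For the secondary endpoints it adds that "success will not be required for determining success of the study". G2 uses step counts, walking and standing durations and related variables to test H3, that PulseFlow improves activity.

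**First recording.** Under F2, Study Day 0: "The PulseFlow device will be given to the subject". At Visit 2, about 48 hours after Visit 1, "activity measurement (body sensor) will be returned", and the boot's own data are downloaded to check compliance. F2 does not say when the first shirt is put on.

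**Second recording.** The Visit 3 text says: "The participant will be asked to return the device at their next visit". That next visit is Visit 4, at about 4 weeks. There, subjects are asked to "wear a comfortable shirt which holds a small activity monitor (PAMSys) for a period of 48 Hours (2 days" and to send the monitor back by courier.

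**Boot status after Visit 4.** H1 ends study treatment at 4 weeks. It moves subjects who are unhealed or not responding to standard of care and a different treatment. It also allows continued use for up to 12 weeks, according to preference and the advice of the treating clinician. The Visit 5 text in F2 expects some continuers.

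**The concern.** H3 asks whether wearing PulseFlow raises activity. To answer it, the two recordings would have to differ in boot wear in a known way: without the boot first, then with it. The visit sequence gives something else. The first window appears to fall after dispensing, so any early effect of wearing the boot is already in the baseline value. The second window follows the visit at which the boot is due back, so an effect of wearing it at week 4 appears only in those who keep it. Others may by then be in replacement footwear or on another treatment.

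G2 states no contrast for H3. Its named confounders (weather, BMI and age, with an open-ended remainder) do not include boot status. No boot-use download after Visit 4 is described. A real gain could be hidden or reversed, and a boot that hinders walking could appear to help. G1 says the results will be used to size a larger superiority trial, so a misread activity signal could carry forward.

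**Working it through.** The documents give no effect size, variance or sample-size derivation for activity, so there is no planned figure to reproduce. The check is the visit sequence, followed by the contrast it implies.

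**Sequence**

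| Event | Timing | Source |
|---|---|---|
| Boot dispensed | Visit 1 | F2, Study Day 0 |
| First sensor returned | Visit 2, about 48 h later | F2, Visit 2 |
| Boot due back | Visit 4, about 4 weeks | F2, Visit 3 |
| Second 48 h worn, sensor couriered back | after Visit 4 | F2, Visit 4 |
| Treatment ends, switches or continues | from 4 weeks | H1; F2, Visit 5 |

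A 48-hour recording handed in 48 hours after Visit 1 fills the interval from Visit 1 to Visit 2. That is an inference. 'The device' in the Visit 3 text is read as PulseFlow, because the activity sensor had already been returned at Visit 2.

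**Possible boot states**
- Nobody continues: on boot, then off boot or on replacement treatment.
- Everybody continues: on boot both times.
- Some continue: on boot, then an unrecorded mixture.

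None of these is no boot followed by boot.

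**Contrast.** None of the following quantities is given in the documents. Let m = mean activity before the device; D0 = wearing effect in the first 48 h; D4 = wearing effect at week 4; G = lasting gain; T = drift unrelated to the boot; S = effect of replacement footwear or treatment; c = share still on the boot after Visit 4. Continuers are assumed to have the average D4.

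- First window: m + D0
- Second window: m + G + T + c·D4 + (1 - c)·S
- Scheduled change: G + T + c·D4 + (1 - c)·S - D0
- Boot effect at week 4: G + D4
- Error (scheduled change minus boot effect): T - D0 - (1 - c)·(D4 - S)

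If H3 meant lasting gain only (G), the error would be T + c·D4 + (1 - c)·S - D0. This too depends on D0, D4, S, T and c.

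**Illustration** (assumed values, in % of pre-device activity). Set D0 = D4 = d and G = S = 0. The change is then T - (1 - c)·d and the error is T - (2 - c)·d. With T = 0:

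| c | d = +10: change (error) | d = -10: change (error) |
|---|---|---|
| 0 | -10 (-20) | +10 (+20) |
| 0.5 | -5 (-15) | +5 (+15) |
| 1 | 0 (-10) | 0 (+10) |

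With d and T each between -10 and +10 and c between 0 and 1, the error runs from -10 - 2·10 = -30 to 10 + 2·10 = +30. It can also be zero: d = T = 10 and c = 1 gives 10 - 10 = 0.

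**If the second window ends at Visit 4, before boot return.** The change becomes G + T + D4 - D0, and the error against the boot effect becomes T - D0. The mixing term is gone, but D0 and T remain. The error need not shrink. With T = S = 0, c = 0.5, D4 = 10 and D0 = -5, the scheduled error is 5 - 0.5·10 = 0, and after the move it is +5.

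**The case against.** The strongest reply is that this is a single-arm proof of concept, activity is a secondary endpoint, and even a perfectly timed before-after change would be confounded with healing and time. All of that stands, and it limits the weight of the point. It does not make the planned contrast interpretable.

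F2 describes itself as a summary, and the protocol attached in Section S is not among the documents, so a start time or return rule may be stated there. J2 also allows a follow-up appointment after consent, which would leave room for an earlier recording. However, no earlier sensor hand-out is described, and a sensor worn before Visit 1 would more naturally come back at Visit 1 than at Visit 2.

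Section D lists adherence to the offloading boot as an assessment, and the list of confounders in G2 is open-ended, so boot status might be used. Coverage after Visit 4 is not stated.

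A reader might infer a direction, for example that the schedule works against PulseFlow. The documents do not support that. If wearing the boot raises activity, the error tends one way; if it lowers activity, the other. H1 lists discomfort as a risk, and at Visit 2 "further device education will be provided in case any issues have risen". Neither is evidence about activity, but neither lets an early negative effect be excluded.

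A reader might also infer that every second recording is off the boot, or that the primary endpoints are compromised. H1 permits continuation, so the first does not follow. The second does not either: "Peripheral perfusion will be measured at baseline, 48 hours, 1 week and 4 weeks" refers to separate measurements, and the timing of the 48-hour sensor recordings does not alter the perfusion, plantar-pressure or safety measurements.

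**Conclusion.** The point holds. Following the plan gives a contrast between activity on the boot and activity in an unrecorded mix of off-boot, replacement-treatment and on-boot subjects. That contrast does not estimate PulseFlow's effect on activity. Neither the size nor the direction of the error can be determined from the documents, and the percentages shown are illustrations only.

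The conclusion rests on three readings: the first recording runs from Visit 1 to Visit 2, the device due back at Visit 4 is PulseFlow, and the unseen Section S protocol does not change the sequence. It concerns only the activity part of H3, a secondary endpoint not needed for study success. It should be fixed because the remedy is cheap, but it does not threaten the study as a whole. It would be too strong to say that moving the second recording restores a comparison with no boot: the early wearing effect stays in the first value, so the H3 claim must be narrowed as well.

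**What to change.** (a) Hand out the second PAMSys at an earlier visit, or mail it with a reminder call, so that its 48 hours end at Visit 4, before any boot return. Collect it in person. The planned boot-data download at each visit should then cover that window, although whether the log is time-stamped is not stated.

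(b) Together with (a), label the first window 'first 48 h on device' and report H3 activity as change over 4 weeks on device. Do not describe it as improvement from a pre-device baseline unless a recording before dispensing can be obtained without altering the treatment schedule.

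(c) Record boot use, and any replacement treatment, for each window, and state the H3 contrast in G2.

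(d) Reconcile the F2 text for Visits 3, 4 and 5 with H1 on boot return and continued use. This review does not choose the rule.

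**Cost.** One hand-out or mailing and one reminder call per subject (the documents give both 15 and 50 subjects), partly offset by dropping the return courier. No extra visit is needed. Handing the sensor out at Visit 3 would tie it up for about 21 days instead of about 2 plus transit: 21 × 15 = 315 against 2 × 15 = 30 sensor-days, or 21 × 50 = 1,050 against 2 × 50 = 100. Mailing it shortly before Visit 4 avoids this. Some windows will be missed because subjects put the sensor on unsupervised. The H3 claim becomes narrower and stays confounded with healing and time.

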This study includes three hypotheses. To examine whether the proposed PulseFlow DF will provide comparable offloading as compared to removable cast walkers measured through a repeated measures study design for in shoe pressures (H1), we will use ANOVA and Fisher's exact tests for intra-subject reduction of peak pressures, pressure time integrals and Dynamic Plantar Loading Index.

To examine whether the proposed PulseFlow DF will help improve macro and micro-circulation in the lower extremity of patients (H2), we will use the similar analytical plan explained above by considering change in Skin perfusion pressure and ABI as dependent variables. For identifying the predictors, we will use multiple linear regression model and Anova (n-way). The independent variables will be severity of neuropathy quantified using Semmes Weinstein Monofilament, the level of activity, BMI, and age.

To examine whether the proposed PulseFlow DF will improve the activity level and quality of life (H3), we will use ANOVA multivariate test. The dependent variables will be number of total steps per day, duration of walking and standing, duration of longest episode of walking (i.e. continuous walking without stop), number of walking episode, duration of sit-to-stand and stand-to-sit postural transition, and SF12. We will use multiple linear regression model and multi-variant test to examine the effect of confounding parameters such as weather condition, BMI, age, etc.

Section H: Potential Risks/Discomforts

H1. Potential Risks/Discomforts

Describe and assess any potential risks/discomforts; (physical, psychological, social, legal, or other) and assess the likelihood and seriousness of such risks:

Some of potential risks could be discomfort, insufficient offloading, and uncomfortable level of compression to your plantar arch. It is important to notify us if you feel discomfort on wearing PulseFlow DF or if you feel excessive pressure to your feet because of wearing the PulseFlow DF.

You should always inspect the wound at each dressing change and comply with instructions providing by your doctor or wound care provider. You should immediately notify us or contact clinic, your doctor, or care provider if you feel the condition of your wound has been deteriorated. The signs of wound deterioration will be discussed with you by your doctor or care provider who treats your wound.

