PulseFlow DF is an adjunct to standard wound healing therapies for the treatment of diabetic foot ulcer. You must comply with the procedures provided by your doctor or care provider for treating your diabetic foot ulcer.

The study device and technology is completely non-invasive, safe, non-toxic and non-ionizing. The potential risks to you are minimal. However, like any battery powered systems, there is a minimum risk of device malfunctioning. In addition, the study devices are not waterproof, and although they use a low powered battery (similar to a cell-phone battery), in order to avoid any risk or shock the provided devices including activity monitor should not be submerged or saturated with fluids during operations or cleaning.

The assessments described above are expected to be minimal risk and probability and magnitude of harm or discomfort anticipated in the research are not greater in and of themselves than those ordinarily encountered in daily life or during the performance of routine physical or psychological examinations or tests

The duration of this study is 4 weeks and thus the treatment using PulseBoot DF will be terminated at 4 weeks. If subject's foot ulcer has not fully healed at 4 weeks, or is deemed not to be responding, they will be switched to standard of care and a different treatment method as instructed by subject's doctor or care provider. Based on subject's preference and advice of subject's doctor or care provider, participants may continue to use PulseFlow DF for up to 12 weeks.

H2. Data and safety monitoring plan

Do the study activities impart greater than minimal risk to subjects?

Yes

NOTE: The answer to the questions in H2 requires the completion of the form: 'Section H – Data and Safety Monitoring Plan' as an attachment in Section S.

H3. Coordination of information among sites for multi-site research

Is the BCM Principal Investigator acting as the SPONSOR-INVESTIGATOR for this multi-site research?

No or Not Applicable

Is BCM the COORDINATING CENTER for this multi-site research?

No or Not Applicable

Section I: Potential Benefits

Describe potential benefit(s) to be gained by the individual subject as a result of participating in the planned work.

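### Device use may run to 12 weeks, but the only planned contact after week 4 is optional and, in the text available, does not ask about infection, serious adverse events or adverse events generally

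*Combined protocol and SAP*

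**What the plan says.** **Duration of use.** Section H1 first says "The duration of this study is 4 weeks and thus the treatment using PulseBoot DF will be terminated at 4 weeks" (I take the device name there to mean the same boot). Participants whose ulcer is unhealed or not responding at that point are to stop: "they will be switched to standard of care and a different treatment method". The same paragraph then allows an exception, on the participant's preference and the clinician's advice: "participants may continue to use PulseFlow DF for up to 12 weeks". Section F2, Visit 3, asks participants to bring the device back at Visit 4.

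**Safety endpoint.** The Primary Safety Endpoints in Section D cover "The occurrence of adverse events during the four (4) weeks of the study treatment" that are possibly, probably or definitely related to the device. The examples given are "deterioration in wound condition such significant increase in wound size, infection, etc, falls, serious adverse events".

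**Contacts.** Section F2 lists an adverse-event assessment at Visit 2 (48 hours) and Visit 3 (1 week). Visit 4 (4 weeks) repeats the baseline assessments and adds a questionnaire. Visit 5 reads "Some participants may be contacted by the study coordinator approximately up to three months post the last study visit to document success of wound healing", and the sentence goes on "if they continue to use PulseFlow DF after 4 weeks as well as potential incident of re-ulceration, or incident of falls".

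**Participant reports.** Section H1 says "It is important to notify us if you feel discomfort on wearing PulseFlow DF or if you feel excessive pressure to your feet". Wound deterioration may be reported to the study team, the clinic, or the participant's doctor or care provider.

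**The concern.** The plan foresees use beyond week 4 and provides for asking whether such use healed the wound. In the text available it makes no matching provision for harm. Visit 5 is optional, and its list leaves out infection and serious adverse events, both of which the safety endpoint names.

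If the plan is followed as written, a device-related infection in week 6 would fall outside the primary safety endpoint and might not be asked about. The reported picture for extended use could then combine healing successes with an incomplete record of harm.

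This matters here because Section E1 classes the research as greater than minimal risk. The protocol's background section also records clinicians' reluctance to use compression where arterial disease may be present. Perfusion, plantar pressure and the other efficacy results are not affected.

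**Working it through.** The plan states no figure on this point, so there is none to reproduce. The check is a comparison of texts plus arithmetic on permitted calendar weeks.

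**1. What Visit 5 covers, against the endpoint's examples**

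| Event named in the safety endpoint | Listed at Visit 5? |
|---|---|
| Wound deterioration | Indirectly, through healing and re-ulceration |
| Infection | No |
| Falls | Yes |
| Serious adverse events | No |

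Visit 5 lists no general adverse-event question, whereas Visits 2 and 3 do.

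**2. Permitted use outside the endpoint window**

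Inputs: endpoint window 4 weeks (Section D); permitted use up to 12 weeks (Section H1). The text does not say whether the 12 weeks include the first four, so both readings are shown for a participant who continues to the limit.

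- 12 weeks in total: (12 − 4)/12 = 8/12 = 67%.
- 12 weeks additional to the first four: 12/(4 + 12) = 12/16 = 75%.

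**3. Timing of Visit 5**

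Input: up to about three months after the last study visit. I take three months as 13 weeks and the last visit as Visit 4, at week 4.

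- Latest contact: 4 + 13 = week 17.
- Delay after the last permitted use: 17 − 12 = 5 weeks, or 17 − 16 = 1 week on the additional reading.
- For comparison, the longest gap between visits in weeks 0-4 is 4 − 1 = 3 weeks (Visit 3 to Visit 4).

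**4. Recall period if contact is made at the end of use**

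- From Visit 4 to the limit of use: 12 − 4 = 8 weeks, or 16 − 4 = 12 weeks.

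All of these are calendar limits. They are not wear time, event rates or shares of the study's total exposure.

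**The case against.** The case on the other side is substantial, and much of it stands.

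- **The endpoint fits the treatment.** A four-week window matches a four-week study treatment, and an endpoint labelled that way claims nothing about later use. This stands, and the window should not change.
- **Continuation looks like the exception.** The device is to be returned at Visit 4, and unhealed or non-responding ulcers are to be switched to other care. This stands, and the number continuing could be zero. But continuation is expressly permitted, and Visit 5 is partly built around it. Asking about healing in continuing users also implies that some may still have open wounds, which fits poorly with the switching rule.
- **Silence is weak evidence.** A reader might infer that nobody is required to ask about adverse events after week 4. The documents do not support that. The safety monitoring plan and the originating institution's protocol are both Section S attachments that were not available, and either may set later reporting rules. The visit lists are not exhaustive either: Visit 4 lies inside the endpoint window and names no adverse-event item. The contents of the follow-up questionnaire and fall log are not shown.
- **Events may surface by other routes.** Section J2 says patients are referred from co-investigators' practices, so a report to the treating clinician may reach the study. The request to notify the team has no week-4 cut-off, and Section L allows extra visits for technical problems. These routes help, but they depend on the participant's initiative or on chance.
- **The risk wording is mixed.** Sections G1 and H1 also describe the risks as minimal. That lowers the urgency. It does not explain why late healing should be recorded and late infection not.

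**Conclusion.** The concern holds in a limited form. Within the text available, late device-related harm in participants who continue may be missed while late healing is collected, because the only planned later contact is optional and its list omits infection, serious adverse events and a general adverse-event question. Whether the gap exists in practice depends on the Section S attachments. Those could add reporting, but as described in Section D the endpoint would still stop at week 4.

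The size is bounded for an individual only: up to 8 of 12 weeks, or 12 of 16 on the additional reading, for someone who continues to the limit. A reader might take the 67% or 75% as the share of the study's device exposure that goes unmonitored. The documents do not support this, since the number who continue and how long they do so are not given. Nor do they show that the four-week endpoint is wrong.

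This is a worthwhile and inexpensive safety improvement. No efficacy conclusion depends on it.

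**What to change.** 1. In Section H1, reconcile the end of treatment at week 4 with the permitted continuation. State that device return at Visit 4 is the default and continuation the exception, and say whether the 12 weeks are total or additional.
2. In Section F2, Visit 5, make the contact mandatory for continuing users, for example: *Every participant who continues with the device will be contacted by the study coordinator at the end of device use and asked about any adverse events, including infection and wound deterioration.* Judge relatedness on the three categories already in Section D.
3. Tell continuing users to report wound deterioration or infection to the study team as well as to their own clinician, so that detection does not wait for the final call.
4. Keep weeks 0-4 as the primary safety endpoint. Report events in the extension separately and descriptively, and label any late healing result as descriptive in self-selected continuing users.
5. If the Section S attachments already contain such rules, a cross-reference may be enough for items 2 and 3.

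**Cost.** Some wording, and one call per continuing participant by the coordinator already named for Visit 5. That is at most 15 calls on the enrolment in Sections D and F1, or 50 on the figure in Section G1. Existing staff would judge relatedness and handle any serious event. The call relies on recall over up to 8 to 12 weeks, which item 3 only partly offsets, and the safety picture may turn out less favourable.
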